FDG	[¹⁸ F]-2-Fluoro-2-deoxy-D-glucose
FN	False Negatives (=test negative in individual with disease)
FNAC	Fine Needle Aspiration Cytology
FP	False Positives (=test positive in individual without disease)
FTC	Follicular Thyroid Carcinoma
Gal-3	Galectin-3: differentiation marker.
GCP	Good Clinical Practice
GDPR	General Data Protection Regulation (in Dutch: Algemene Verordening Gegevensbescherming (AVG))
GLUT	Membrane-bound Sodium-independent Glucose Transporters
HIF-1α	Hypoxia Inducible Factor – 1 alpha: hypoxia marker
HK	Hexokinase
HRQoL	Health Related Quality of Life
IB	Investigator's Brochure
IC	Informed Consent
ICER	Incremental cost-effectiveness ratio
iMCQ	Medical Consumption Questionnaire
IMP	Investigational Medicinal Product
IMPD	Investigational Medicinal Product Dossier
iNMB	Incremental Net Monetary Benefit
iPCQ	Productivity Cost Questionnaire
Ki67	Marker of mitosis (=MIB)
LR-	Negative Likelihood Ratio (Bayesian test characteristic)
LR+	Positive Likelihood Ratio (Bayesian test characteristic)
MC	Medical Centre
METC	Medical research ethics committee (METC); in Dutch: medisch ethische toetsing
	commissie (METC)
MIB	Marker of mitosis (=Ki67)
mRNA	Messenger Ribonucleic Acid
N/A	Not Applicable
Nal	Sodium Iodine transporter
NNT	Number Needed to Treat
NPV	Negative Predictive Value (Bayesian test characteristic)
OR	Odds Ratio (Bayesian test characteristic)
OS	Overall Survival
PALGA	the nationwide network and registry of histo- and cytopathology in The Netherlands

PET +ve	FDG-PET/CT positive					
PET -ve	FDG-PET/CT negative					
PET/CT	Positron Emission Tomography / Computed Tomography					
PFS	Progression-Free Survival					
PI	Principal Investigator					
PPV	Positive Predictive Value (Bayesian test characteristic)					
Prev	Prevalence					
PTC	Papillary Thyroid Carcinoma					
RCT	Randomised Controlled Trial					
Se	Sensitivity (Bayesian test characteristic)					
SF-36	Short Form Health Questionnaire					
SOP	Standard Operating Procedure					
Sp	Specificity (Bayesian test characteristic)					
SPC	Summary of Product Characteristics (in Dutch: officiële productinfomatie IB1-tekst)					
Sponsor	The sponsor is the party that commissions the organisation or performance of the					
	research, for example a pharmaceutical					
	company, academic hospital, scientific organisation or investigator. A party that					
	provides funding for a study but does not commission it is not regarded as the					
	sponsor, but referred to as a subsidising party.					
STN	Solitary Thyroid Nodule					
SUSAR	Suspected Unexpected Serious Adverse Reaction					
SUV	Standardised Uptake Value. Parameter expressing the amount of FDG-uptake with					
	respect to patient size (body weight, body surface area or lean body mass) and					
	administered activity. A SUV of 2 implies concentration of FDG twice the amount					
	as can be expected from even distribution throughout the body.					
Tg	Thyroglobulin: differentiation marker for thyroid cells					
TLG	Total Lesion Glycolysis: area under the volume-SUV histogram					
TN	True Negatives (=test negative in individual without disease)					
TP	True Positives (=test positive in individual with disease)					
US	UltraSonography					
VAS	Visual-Analogue Scale					
WGBO	Law on Medical Treatment Agreement (in Dutch: Wet op de Geneeskundige					
	BehandelingsOvereenkomst)					
WMO	Medical Research Involving Human Subjects Act (in Dutch: Wet Medisch-					
	wetenschappelijk Onderzoek met Mensen					

LIST OF FIGURES AND TABLES

Figures

Figure 1: Flow-chart of the trial
Figure 2: Relation between study size (N), study-arm size sizes (n_1 and n_2) and effect size.
Empirical relation: N=16.33935*ES ^{-1.86986} , R ² =.999443). Expected ES=73.1%-40.3%=32.8%
Figure 3: Position of the normal thyroid
Figure 4: Topograms showing the major landmarks: the meatus acusticus externus (MAE), the
fossa jugularis sternalis (FJS) and the lower margin of the arcus aortae (LAA)50
Figure 5: Example of a FDG-PET/CT positive thyroid nodule in the isthmus, which proved to
be a 10 mm differentiated papillary thyroid carcinoma (pT1a cN0M0)51
Figure 6: Anatomy and subdivision of the normal thyroid gland54
Figure 7: Cumulative Binomial Distribution for a sample size of 22 (interim-analysis) or 44 (end-
of-study evaluation) for an individual patient probability of a false-negative FDG-PET/CT of
0.05. In case that more than 4/22 patients (18.2%) at time of the interim analysis or 6/44
(13.6%) patients at time of the end-of-study evaluation have a false-positive FDG-PET/CT (in
the control study arm), the false-negative probability is larger than the maximum accepted
value of 0.05
Figure 8: Results from meta-analysis on test characteristics of FDG-PET/CT in indeterminate
thyroid noudles [4]. CI: confidence interval; FE: fixed-effects; FN: false negative; FNAB: fine-
needle aspiration biopsy; FP: false positive; LR-: negative likelihood ratio; LR+: positive

Rationale: Only about ¹/₄ of patients with thyroid nodules with indeterminate cytology are proven to suffer from a malignancy at diagnostic hemithyroidectomy. Therefore $\sim \frac{3}{4}$ is operated upon unbeneficially. Recent studies using FDG-PET/CT have suggested that it can decrease the fraction of unbeneficial procedures from ~73% to ~40%. Thereby the direct costs per patient, the number of hospitalization and average sick leave days might decrease and the experienced HRQoL might increase. A study will be undertaken to show the additional value of FDG-PET/CT after indeterminate cytology with respect to unbeneficial procedures, costs and utilities. Main objective: To determine the impact of FDG-PET/CT on decreasing the fraction of patients with cytologically indeterminate thyroid nodules undergoing unbeneficial patient management. Study design: A prospective, multicentre, randomised, stratified controlled blinded trial with an experimental study-arm (FDG-PET/CT-driven) and a control study-arm (diagnostic hemithyroidectomy, independent of FDG-PET/CT-result). Study **population:** Adult patients with a cytologically indeterminate thyroid nodule, without exclusion criteria, in 15 (university and regional) hospitals distributed over the Netherlands. Intervention: One single FDG-PET/low-dose non-contrast enhanced CT of the head and neck is performed in all patients. Patient management depends on allocation and results of this FDG-PET/CT. Main study parameters/endpoints: The number of unbeneficial interventions, i.e. surgery for benign disease or watchful-waiting for malignancy. For secondary objectives: complication rate, consequences of incidental PET-findings, number of hospitalisation and sick leave days, volumes of healthcare consumed, experienced HRQoL, genetic, cytological and (immuno)histopathological features of the nodules. Sample size calculation/data analysis: Based on above-mentioned estimated reduction in unbeneficial interventions from ~73% to ~40%, at least 90 patients with nodules>10 mm need to be analysed (2:1 allocation, α =0.05, power=0.90, one-tailed Fisher's exact test). After correction for nodule size and data-attrition, 132 patients need to be included in total. Intention-to-treat analysis will be performed. Incremental Net Monetary Benefit based on the total direct costs per patient and the gain in HRQoL-adjusted survival years are computed. Cytological, histological and genetic parameters and their correlation to FDG-avidity will be described. Nature and extent of the burden and risks associated with participation, benefit and group relatedness: All patients undergo one FDG-PET/CT scan of head/neck (effective dose: <3.5 mSv) and are asked to fill in 6 questionnaires at 4 time points. FDG-PET/CT negative patients in the experimental arm will undergo a single confirmatory US (±FNAC). An interim/posterior analysis of the control subjects is performed to ensure oncological safety. In case of an unexpected high false-negative ratio in this control arm, all patients will be advised to undergo surgery.

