4.4 Sample size calculation

Based on the main objective, it is expected that FDG-PET/CT can reduce unjust treatment from ~73.1% (=136/186 benign lesions >10mm) to ~40.3% (=75/186 false-positive and false-negative lesions >10mm, §1.3, p19). Using G*Power version 3.1.9.2. (and validated using JMP from SAS version 9.0.1, STATA version 12.0SE and PASS version 2011), we computed using an α error probability of 0.025 (=0.05/2, Bonferroni correction for interim analysis) a power of 0.80 and an allocation ratio of N_A:N_B=2:1, we need to include at least 90 patients in total (one-tailed test) to establish this difference (60+30 patients in arm A and B respectively).

Since around 82.7% (=186/225, §1.3, p19) fulfil the size criterion, at least 111 patients (74+37 patients in arm A and B respectively) need to be included. Accounting for additional 15% data loss at the final end-point, 132 patients should be included (88+44 patients in arm A and B respectively) (Figure 2, p40).

This total number of patients could at best (assuming no data loss) discern a reduction of 26.6% unjust treatment in the whole population with an actual α error probability of 0.016 and a power of 0.80. This is based on a reduction from 74.2% (prevalence of benign disease in all 225 patients) to 47.6%. In the experimental arm (88 patients), where the number of false-negative PET is estimated to be ~1.3% (3/225), this number of patients should establish a false-negative rate of maximal 7.5% (actual α error probability of 0.0066 and a power of 0.80). All analyses will be performed according to the intention-to-treat principle, meaning that analysis is based on the initial study-arm allocation and not on the treatment eventually received (e.g. a FDG-PET/CT negative patient in the experimental arm does not refrain from surgery and therefore actually is treated according to the control study arm).

[figure not shown]

Figure 2: Relation between study size (N), study-arm size sizes (n₁ and n₂) and effect size. Empirical relation: N=16.33935*ES^{-1.86986}, R²=.999443). Expected ES=73.1%-40.3%=32.8%

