10.3 Univariate analysis

All comparisons will be made using the general requirements for relating research questions as stated in Table 6, p66.

Characteristics of (independent) study-arms will be compared using either t-tests ((log)normal) or Wilcoxon rank-sum tests for continuous variables (e.g. age, SUV, hospitalisation days, volumes of care used, questionnaire scores). For categorical data either Fisher exact tests or χ^2 tests will be used (e.g. sex, unbeneficial patient management).

With respect to the primary research question, fractions unbeneficial patient management therefore will be compared using Fisher exact tests or χ^2 tests.

Relations between variables will be univariately described by the parameters from Table 7, p66. These parameters are compared using the tests from Table 8, p67.

Scale:	Groups:	Dependency:	Group Size:	Distribution:	Test:
Continuous	1	n/a	n≥30	(Normal)	t-test
(and			n<30	Normal	_
categorical ordinal)				Not normal but transformable	Transform than t-test
				Not normal, not transformable	Sign test
	2	Independent	n≥30	(Normal)	t-test
	-	n<30		Normal, equal variances	
				Normal, non-equal variances, equal n's	-
				Normal, non-equal n's, transformable	Transform than t-test
				Normal, non-equal variances, non-equal n's, not transformable	Wilcoxon rank-sum tes (= Mann-Whitney U test
				Not normal, transformable	Transform than t-test
				Not normal, not transformable	Wilcoxon rank-sum tes (= Mann-Whitney U test
		Dependent	n≥30	(Normal)	Paired t-test
			n<30	Normal	_
				Not normal, transformable	_
				Not normal, not transformable	Wilcoxon signed ranks
	≥3	Independent	n/a	Normal, 1 factor	One-Way ANOVA
				Normal, ≥2 factors	Two-Way or othe ANOVA
	_		Not normal	Kruskal-Wallis for Factor (+Dunn's posthoo test)	
		Dependent	n/a	Normal	Repeaed Measures
				Not normal	Friedman ANOVA
Categorical (Nominal)	1		np≥5 and n(1- p)≥5		z-approximation
	2	Independent	Expected cell frequencies <5		Fisher's Exact Test
≥3	_		Expected cell frequencies ≥5		X ² or z-approximation
		Dependent			McNemar or ĸ
	≥3	Independent	Expected cell frequencies <5		Collapse categories fo X^2
			Expected cell		X ²
			frequencies ≥5		

Table 6: General Requirements for selection of Statistical tests used for univariate analysis (comparison)

Predicting each other	Parameter:
	Relative Risk
	Spearman's ρ squared
yes	Regression
no	Pearson's Correlation R squared (log)normal
	Spearman's p squared (not-normal)
	yes

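### The Summary and §4.4 justify the same 90 patients with different α and power; only §4.4's pair reproduces, and the primary significance level is left open

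*Protocol*

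**What the plan says.** The Summary, under sample size and data analysis, states that "at least 90 patients with nodules>10 mm need to be analysed" and gives the basis as 2:1 allocation, an α of 0.05 and "power=0.90, one-tailed Fisher's exact test". After allowing for nodule size and attrition it arrives at 132 enrolled.

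Section 4.4 reaches the same 90 and 132 from the same reduction (73.1% to 40.3%), also one-tailed and 2:1. Its error rates differ: an "α error probability of 0.025 (=0.05/2, Bonferroni correction for interim analysis"), and "a power of 0.80 and an allocation ratio of" 2:1. It concludes that "we need to include at least 90 patients in total (one-tailed test) to establish this difference", split 60+30.

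Section 10.3, on the primary question, says that "fractions unbeneficial patient management therefore will be compared using Fisher exact tests" or χ² tests. It names no level. Section 8.7 describes the interim analysis: a count of false-negative scans among the first 22 control patients, judged against a 5% rate with its own α of 0.025.

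**The concern.** One sample size, for one endpoint, effect, allocation ratio and one-tailed test, cannot correspond to both pairs of error rates. At least one statement is wrong, and two things follow.

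First, the power printed in the Summary, which most readers and funders will cite, may not be what the design delivers.

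Second, the level at which the main conclusion will be judged is uncertain. A one-sided p-value between 0.025 and 0.05 meets the Summary's level and misses that of §4.4. The reason §4.4 gives for 0.025 does not settle this. It is a Bonferroni correction for the interim analysis, but that interim never compares the arms on the primary endpoint and so uses none of its α. A reader who notices this could reasonably go back to 0.05.

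**Working it through.** **Inputs (§4.4).** Control rate 136/186 = 0.731; experimental rate 75/186 = 0.403; 60 patients in arm A and 30 in arm B; one-tailed Fisher's exact test.

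**Method.** With x unbeneficial cases among 60 in arm A and y among 30 in arm B, the one-sided Fisher p-value is the hypergeometric lower tail P(X ≤ x), given x + y events among 90. Power is the sum of Bin(x; 60, 0.403) × Bin(y; 30, 0.731) over all pairs with p ≤ α.

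**Reproducing §4.4.** At α = 0.025 the power is 0.801. Searching over 2:1 designs, 90 is the first total to reach 0.80. Section 4.4 is reproduced exactly.

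**Testing the Summary.** One-sided Fisher power by analysed total:

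| Analysed (A+B) | α = 0.05 | α = 0.025 |
|---|---|---|
| 90 (60+30) | 0.877 | 0.801 |
| 93 (62+31) | 0.893 | 0.825 |
| 96 (64+32) | 0.907 | 0.830 |
| 117 (78+39) | 0.946 | 0.901 |

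- At the Summary's own α, 90 patients give 0.877, just over 2 points short of 0.90 (0.900 − 0.8765 = 0.0235). The Summary's rounded rates of 73% and 40% give 0.880.
- Power of 0.90 needs 96 analysed at α 0.05, or 117 at α 0.025. Applying the protocol's 82.7% size fraction and 15% loss, 96/(0.827 × 0.85) = 136.6 and 117/(0.827 × 0.85) = 166.4. Rounded up to keep 2:1, that is about 138 and 168 enrolled, not 132.
- The 132 enrolled are expected to yield 132 × 0.85 × 0.827 ≈ 93 evaluable. Power at 93 is still below 0.90 at either level.

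**Effect on the decision.** Take 22/30 (73%) unbeneficial in the control arm, close to the planned rate:

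| Arm A | Reduction | One-sided Fisher p | At 0.05 | At 0.025 |
|---|---|---|---|---|
| 29/60 | 25.0 points | 0.020 | pass | pass |
| 30/60 | 23.3 points | 0.028 | pass | fail |
| 31/60 | 21.7 points | 0.039 | pass | fail |
| 32/60 | 20.0 points | 0.054 | fail | fail |

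**Type I error.** Because Fisher's test is conservative, its actual size at 60+30 with a common rate of 50% is 1.5% for nominal 0.025 and 3.1% for nominal 0.05. The real false-positive risk therefore roughly doubles, as the nominal one does.

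**Which test.** Table 6 sends comparisons with expected cells of at least 5 to χ². At the planned rates the pooled proportion is (60 × 0.403 + 30 × 0.731)/90 = 0.513, and the smallest expected cell is 30 × (1 − 0.513) ≈ 14.6. Table 6 thus points to χ², although Fisher's test was powered. Exact power of the uncorrected one-sided χ² at 60+30 is about 0.92 at α 0.05 and 0.85 at α 0.025.

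**The case against.** Section 4.4 writes 0.025 as half of 0.05, so the Summary's 0.05 may be the overall level before the split. That is a fair reading and it softens the α conflict. It does not help the power figure: 0.90 would then stand against a delivered 0.80.

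An uncorrected χ² test, which §10.3 permits, gives about 0.92 at one-sided 0.05, so the Summary's power could be met with a different test. However, the Summary names Fisher's test, and at 0.025 χ² reaches only 0.85.

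Both statements are planning inputs, not declared rules for success, and a statistical analysis plan may set the level and sidedness. That is true, and the silence of §10.3 is not counted here as a fault. The point rests on two statements that the protocol does make and that conflict. An analysis plan could inherit either one.

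Recruitment is complete at 132, and that number follows from §4.4, so no enrolment decision depends on the Summary. This stands, and no more patients are asked for.

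Finally, if the Bonferroni reason falls away, the protocol's own logic leads back to 0.05, so reproducing 90 does not prove which level the sponsor intends for the final test. This also stands. It is why the level has to be stated outright and not inferred.

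**Conclusion.** The concern holds. The Summary's pair (one-sided α 0.05, power 0.90) is wrong for 90 patients and Fisher's test: the power is 0.877 at its own α and 0.801 at the α in §4.4. Section 4.4's pair (0.025, 0.80) reproduces 90 exactly, so the sample size itself is sound. As written, the protocol leaves the primary level open between 0.025 and 0.05, and reductions of about 22 to 23 points, which are plausible here, fall between the two.

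These figures rest on the protocol's assumed rates, 60+30 analysed patients and the one-tailed Fisher test. The remarks on Table 6 and on what §10.3 omits are secondary, and the conclusion does not depend on them.

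**What to change.** Correct the Summary to one-sided α 0.025, power 0.80, Fisher's exact test, in line with §4.4. State once, in §10.3 or by reference to §4.4, that the primary comparison is judged at one-sided 0.025, and name the single test to be used. Remove the Bonferroni reason from §4.4, since the interim in §8.7 does not test the primary endpoint; one-sided 0.025 can be kept as the chosen level without it. A two-sided 95% confidence interval for the risk difference would match that level and is a useful addition.

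If the sponsor prefers one-sided 0.05, the protocol should say so and justify it, and the power for 90 patients under Fisher's test should be given as about 0.88.

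The cost is wording only: 90 and 132 do not change, and one published figure becomes less favourable. Since §4.5 records that all 132 patients are included, with last data due in November 2019, the level should be fixed before the primary comparison is seen.

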
1. INTRODUCTION AND RATIONALE

1.1 Introduction and problem description

Differentiated thyroid carcinoma (DTC) is rare (incidence: ~13-31/million patient years [1]). Although the prognosis is favourable, its morbidity is high. As most patient present with a palpable thyroid nodule (TN), with a lifetime prevalence of 3-8%, and the chance of cancer in any such a nodule is less than 5%, screening for cancer is warranted once a nodule is established. The prevalence of TNs increases with age. Nowadays, due to the increasing use of ultrasound (US) and other imaging techniques more and more asymptomatic TNs are discovered, the majority of which have no clinical relevance. As initial instrument, (US guided) fine-needle aspiration cytology (FNAC) is recommended. Aspirates are classified in six diagnostic categories according to the Bethesda System for Reporting Thyroid Cytopathology (Appendix III: The Bethesda System for Reporting Thyroid Cytopathology, §15.3, p91) [2, 3]. In about 75% of patients, this will lead to a definite diagnosis and treatment: either benign (Bethesda category II), suspicious (V) or definite malignant (VI). However in the remaining cases, repetitive FNAC cannot determine whether the lesion is benign or malignant, due to cellular atypia (III), follicular neoplasia (V) or repetitive nondiagnostic or unsatisfactory specimens (I). According to current practice, in all these patients diagnostic surgery is performed to reach a final histological diagnosis [4-6]. In about 69-88% these patients, the nodule is benign, and surgery was therefore futile. Especially in case the nodule was asymptomatic, the surgery was unbeneficial. Apart from symptoms and cosmetic complaints of the neck scar, about up to one third of these patients need lifelong daily thyroid hormone suppletion. Furthermore, although rare, surgical complications may be severe (haemorrhage, infection, permanent hoarseness) [7-9]. Finally, surgery, hospitalisation and sick-leave are costly. In most malignant thyroid nodules (~20-25% of operated patients), secondary surgery with adjuvant treatment including radio-active I-131 thyroid remnant ablation, has to be performed. Only in case of subcentimetre, indolent, unifocal papillary microcarcinoma (UPM), additional treatment is unnecessary.

1.2 FDG-PET/CT

The proposed study capitalizes on one of the assets of positron emission tomography using the radiofluorinated glucose analogue FDG (FDG-PET/CT): this technique cannot only visualize but can also quantify FDG-uptake and thus is able to distinguish metabolically (glycolytic) highly active tissue from less active tissue. It offers an opportunity for non-invasive, in vivo tissue characterization and could play a role in further characterisation of lesions. As many factors can influence the extent of FDG-uptake, the underlying mechanics of FDG-

accumulation in tissue, are still a matter of debate. This is addressed in this proposal as a secondary objective. A variety of mechanisms have been proposed for accelerated glucose use in tissue: tumour cells predominantly rely on anaerobic (lactate producing) glycolysis instead of mitochondrial oxidative phosphorylation, even in the presence of oxygen (Warburg effect). To support the necessary high rate of glycolysis, cells need an increased transport of glucose in the cells, facilitated by upregulation of sodium-dependent membrane-bound glucose transporters (GLUTs). Glucose transport activity can be regulated by alterations in the expression of GLUT and by post-translational mechanisms, including transporter translocation to plasma membranes. Increased concentration of the first enzyme in the glycolytic pathway (hexokinase, HK) with decreased rates of the gluconeogenesis enzyme glucose-6phosphatase are considered to accelerate glucose phosphorylation and thus enhanced FDGtrapping. FDG-uptake has been correlated with tumour doubling time and proliferation rates, and in thyroid carcinoma FDG-uptake is correlated with tumour aggressiveness and dedifferentiation. Yet, it is currently unknown exactly which underlying tissue gene alterations are related to FDG-uptake in benign or malignant thyroid lesions. Finally, the presence of (FDG-avid) inflammatory cells might be confounding, since these may have a major impact on FDG-uptake. At present it is still poorly elucidated which of these and other factors contribute to FDG-uptake in thyroid lesions.

The limited spatial resolution of a PET-scanner, may lead to underestimation of the true FDGuptake in smaller lesions, generally smaller than 2-3 times the resolution which is about ~3 mm full width at half maximum (FWHM) in state-of-art scanners and ~5 mm FWHM in previousgeneration scanners. As most palpable thyroid nodules are larger than 10 mm and both the risk of malignancy in these nodules is much smaller and the clinical relevance of UPMs are limited, we will focus primarily on lesions larger than 10 mm. As previously mentioned, thyroid US is able to detect even smaller nodules.

FDG-PET/CT is an established and cost-effective procedure for a number of indications. FDG-PET/CT is non-invasive and has no known adverse events related to the administration of FDG. The effective patient dose of a *head and neck* FDG-PET/CT for a healthy 70 kg adult is less than 3.5 mSv, much lower than a diagnostic CT of the head and neck. A PET/CT-scanner is widely available and accessible for all patients in the Netherlands.

